### **6.1.1 Screening Visit (-7 days before start of Research Intervention)**

- Informed consent
- Medical history
- Medication history

### **6.1.2 Intervention Phase (Phase III)**

Eligible subjects will be randomly assigned to one of the arms using a computer-generated randomization scheme developed by the data manager.

#### **6.1.2.1 Visit 1 (end of study)**

Collection of pain score questionnaires and narcotic consumption.

### **6.1.3 Follow-up Phase**

Participant recorded questionnaires and data will be obtained at the standard surgical follow-up visit.

## **7. Study Intervention**

### **7.1 Study Intervention/Device Description**

Gabapentin will be prepared in a capsule format. It will be shipped to the PI's address at Weill Cornell. The drug may be stored at room temperature which will be indicated on the product label.

The placebo will also be prepared in a capsule format. It will be shipped to the PI's address at Weill Cornell. The drug may be stored at room temperature which will be indicated on the product label.

The exact shipping address is below:

Research Pharmacy #PH#  
NewYork-Presbyterian Hospital/Weill Cornell Medical Center  
[name]  
[name]

### **7.2 Availability**

The use of gabapentin in this study is considered investigational as it is used for an unapproved indication.

Gabapentin is an investigational agent supplied to investigators by Curis Pharmacy.

### **7.3 Acquisition and Accountability**

Contact person:

[name] @ Curis Pharmacy  
[name]  
[name]  
[name]

[contact]- [contact].

Time necessary to fill order depends on quantity needed. Two day priority shipping is available.

Agent Inventory Records/Device Logs – The investigator, or a responsible party designated by the investigator, will maintain a careful record of the inventory and disposition of all agents/device received from *Sponsor* on a Drug Accountability Record Form (DARF) or Device Log.

#### **7.4 Formulation, Appearance, Packaging, and Labeling**

Both the gabapentin and placebo will be identical appearing capsules. The appearance will be blue Opaque capsules. The packing will vary based on quantity ordered (ie. larger quantities will be sent in unguator jars). Pills will be labelled generically to ensure blinding.

#### **7.5 Product Storage and Stability**

Product will be stored at room temperature.

#### **7.6 Preparation**

No preparation is needed, the capsules are ready for oral use.

#### **7.7 Dosing and Administration**

Each participant will receive the same dose of the drug.

Gabapentin will be administered as a single dose pre-operatively 600 mg and then 300mg three times a day for three post-operatively.

Placebo medication will be administered in the same fashion.

##### **7.7.1 Dosing Delays/Dose Modifications**

If a subject demonstrates side effects, the dose will be reduced to half. If there is a significant adverse event, the drug will no longer be administered.

#### **7.8 General Concomitant Medication and Supportive Care Guidelines**

All concomitant medications will be recorded and/or updated on subject medication log in keeping with routine clinical practice and saved in subject binder, if applicable.

### **7.9 Duration of Therapy and Criteria for Removal from Study**

In the absence of delays in administration of the investigational drug due to adverse event(s), drug administration may continue in the post-operative period for three days addition to the pre-operative period. Other reasons may include:

- Intercurrent illness that prevents further administration of investigational drug,
- Unacceptable adverse event(s)
- Subject decides to withdraw from the study, or
- General or specific changes in the subject's condition render the subject unacceptable for further administration of drug in the judgment of the investigator

### **7.10 Duration of Follow Up**

Subjects will be followed until their first post-operative visit, at which time they will be removed from the study, or until death, whichever occurs first. Subjects removed from study for unacceptable adverse events will be followed until resolution or stabilization of the adverse event.

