### **8.1 Discontinuation of Study Intervention**

Discontinuation from gabapentin administration does not mean discontinuation from the study, and remaining study procedures should be completed as indicated by the study protocol. If a clinically significant finding is identified (including, but not limited to changes from baseline) after enrollment, the investigator or qualified designee will determine if any change in participant management is needed. Any new clinically relevant finding will be reported as an adverse event (AE).

The data to be collected at the time of study intervention discontinuation will include the following:

- Post-operative follow-up to ensure any adverse event resolution

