### **8.2 Participant Discontinuation/Withdrawal from the Study**

Participants are free to withdraw from participation in the study at any time upon request.

An investigator may discontinue or withdraw a participant from the study for the following reasons:

- Significant study intervention non-compliance
- If any clinical adverse event (AE), laboratory abnormality, or other medical condition or situation occurs such that continued participation in the study would not be in the best interest of the participant
- If the participant meets an exclusion criterion (either newly developed or not previously recognized) that precludes further study participation
- Participant unable to receive the medication
- Participant lost to follow-up after several attempts to contact subject to schedule study visit.

Subjects will be medically monitored by clinicians in the research team for detection of any adverse events. The reason for participant discontinuation or withdrawal from the study will be recorded on the Case Report Form (CRF). Subjects who sign the informed consent form and are randomized but do not receive the study intervention may be replaced. Subjects who sign the informed consent form, and are randomized and receive the study intervention, and subsequently withdraw, or are withdrawn or discontinued from the study, will not be replaced.

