## **12.2 Statistical Analysis**

The primary objective of this double-blind, placebo controlled randomized trial is to compare the participant-reported pain scores taken on an 11-point numerical rating scale (NRS-11) between subjects who received Gabapentin and controls who received placebo on day-7 post-scrotal surgery. The secondary objective is to determine whether the addition of gabapentin for post-operative pain control reduces narcotic intake. This study will also explore the effect gabapentin has on symptom modification.

Assuming a baseline NRS-11 score of 3.8 (from previous study) and a goal is to detect a two-point difference (reduction) in the day-7 pain score between the two groups, a sample size of 86 participants (43 per arm) will yield a power of 80% when using a two-sample t-test with a 0.05 two-

sided significance level. To account for potential loss to follow up and drop-out at a rate of 25%, each arm will require 43 study participants for a total recruitment of 86 study participants. This calculation assumes a standard deviation of 2.9, which is based on a previous study that looked at the effect of celecoxib in the same patient setting.

Approximately 150 to 250 microTESE procedures are conducted at our site annually. As a result, we plan to accrue and complete the study in 29 months (i.e. ~9 study participants per month).

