Descriptive statistics will be calculated to describe the cohort of study participants using N (%) and mean, median, range for categorical and continuous factors, respectively. A two-sample t-test or nonparametric Wilcoxon rank-sum test will be used, as appropriate, to compare the mean (median) participant-reported pain scores on day 7 post-scrotal surgery between the two arms. A chi-square test or Fisher's exact test will be used, as appropriate, to compare the proportion of narcotic use post-scrotal surgery between the two arms and to compare the proportion of adverse events experienced post-scrotal surgery between the two arms. Similar analyses will also be completed on the NRS-11 pain score, narcotic use, and reported adverse events on day-1 post-scrotal surgery. Generalized estimating equations (GEE) modeling will also be performed to compare NRS pain scores, assessed over all post-operative days 1 to 7, between the gabapentin and placebo groups. GEE allows for multiple observations per participant (i.e., pain scores for day 1 to day 7, per participant) and also allows for the incorporation of missing pain scores at some of the defined time points.

All p-values will be two-sided with statistical significance evaluated at the 0.05 alpha level. Ninety-five percent confidence intervals for all parameters of interest will be calculated to assess the precision of the obtained estimates. All analyses will be performed in R Version 3.6.1 (R Foundation for Statistical Computing, Vienna, Austria). Note: The statistical considerations section was written in conjunction with [name], MS, in the Division of Biostatistics and Epidemiology, Department of Healthcare Policy & Research.

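### Sections 7.9, 7.10, 8 and 8.2 do not separate stopping study drug from leaving the study, as 8.1 does, so day-7 pain and later narcotic counts can be lost when drug stops

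*Combined protocol and SAP*

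**What the plan says.** Five places in the combined protocol and SAP bear on a man whose study drug is stopped.

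- **Section 7.9.** The heading covers both duration of therapy and removal from the study. The text beneath it is about whether drug can go on being given, and unacceptable adverse events are among its reasons.
- **Section 7.10.** "Subjects removed from study for unacceptable adverse events will be followed until resolution or stabilization of the adverse event". Pain and narcotic outcomes are not mentioned for these men.
- **Section 8 (opening text).** Certain events, severe sedation and dizziness among them, lead either to stopping the intervention or to withdrawal. The text does not say which. Men who stop the intervention may stay for safety and efficacy endpoints, where applicable.
- **Section 8.1.** "Discontinuation from gabapentin administration does not mean discontinuation from the study, and remaining study procedures should be completed". The one item it lists for collection at discontinuation is "Post-operative follow-up to ensure any adverse event resolution".
- **Section 8.2.** The investigator may withdraw a man from the study for reasons that include "Significant study intervention non-compliance" and "Participant unable to receive the medication". Dosed men who are withdrawn are not replaced.

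The analysis is in section 12.2: a two-sample t-test or Wilcoxon test on day-7 pain. No analysis population is defined. The only remark on missing scores concerns the GEE model over days 1 to 7.

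**The concern.** The same event, being unable or unwilling to go on with the capsules, can end participation under one section and leave it intact under another. Two staff members could handle the same man differently, and each could point to text in support.

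This matters because dosing ends three days after surgery, while the comparison that sizes the trial is at day 7. A man taken off study when his drug stops has no score for that test, and his later tablet counts go too. Stopping for sedation or dizziness can be a consequence of the assigned arm, since section 13.1.1 lists dizziness and somnolence as exceeding placebo. Blinding does not prevent removal that side effects themselves bring about. If loss differs by arm and is related to pain, the day-7 comparison no longer estimates the difference between the groups as randomised.

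**Working it through.** **1. The passages applied to one man.** His capsules are stopped on post-operative day 1 for an adverse event.

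| Section | Does he stay in the study? | Outcome data named |
|---|---|---|
| 7.9 | Heading suggests removal; body concerns drug | None |
| 7.10 | Treated as removed | Adverse-event follow-up only |
| 8 | Either; may stay | Safety and efficacy, where applicable |
| 8.1 | Yes, with remaining procedures | Adverse-event follow-up listed |
| 8.2 | May be withdrawn | None |

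These do not yield one answer on whether his pain and narcotic surveys continue.

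**2. The plan's own figure.** From section 12.2: "a goal is to detect a two-point difference (reduction) in the day-7 pain score between the two groups", SD 2.9, and "All p-values will be two-sided with statistical significance evaluated at the 0.05 alpha level". The size claim is "a sample size of 86 participants (43 per arm) will yield a power of 80% when using a two-sample t-test", with a 25% loss allowance that is not split by arm.

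- Normal approximation: n = 2(1.960 + 0.842)² × 2.9² / 2² = 33.0, rounded up to 34 per arm. The exact noncentral t also gives 34 (power 80.0%).
- 34 × 1.25 = 42.5, rounded up to 43 per arm, 86 in total. This reproduces the plan.
- Power is 88.5% with 43 per arm analysed, and 77.5% with 32 per arm (43 × 0.75 = 32.25).

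The present point does not depend on how the 25% was applied.

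**3. Illustrative bias.** Let L_G and L_P be the proportions removed on gabapentin and placebo. Let s be how much higher removed men would have scored on day 7 than retained men. In each arm the full mean equals the retained mean plus L × s, so

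bias in (gabapentin − placebo) = −s × (L_G − L_P).

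Neither the losses nor s is in the documents. Losses of 10%/5%, 20%/5% and 30%/10%, and s of 1 to 2 points, are assumptions. The last two columns use the noncentral t with SD 2.9 and the analysed numbers shown.

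| L_G / L_P | Analysed | Bias, s = 1 | Bias, s = 2 | Type I error, s = 1 to 2 | Power for 2 points, no bias |
|---|---|---|---|---|---|
| 10% / 5% | 39 v 41 | −0.05 | −0.10 | 5.1% to 5.3% | 86.1% |
| 20% / 5% | 34 v 41 | −0.15 | −0.30 | 5.6% to 7.2% | 83.5% |
| 30% / 10% | 30 v 39 | −0.20 | −0.40 | 5.9% to 8.7% | 79.9% |

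The sign favours gabapentin only because s is taken as positive. If removed men would have scored lower, the sign reverses. If losses are equal and s is the same in both arms, the bias in the difference is zero.

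**The case against.** The strongest reply is that the protocol already keeps these men. Section 8.1 says so plainly, and the remaining procedures it refers to include the surveys through day 7. Its single listed item concerns the moment of discontinuation and does not cancel those surveys. Section 7.9's body is about giving drug, and 7.10 can be read as extending safety follow-up rather than ending other follow-up. This has weight: stopping surveys for every man who stops drug would defeat 8.1. But 7.10 still presupposes removal for adverse events, section 8 makes staying optional, and 8.2 leaves withdrawal to discretion. The conflict remains.

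Several stronger readings are tempting and are not supported.

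- *The protocol requires removal for intolerance or non-compliance.* Non-compliance appears only in 8.2, which is permissive. The ground of being unable to receive the medication may be meant for men never dosed, whom 8.2 discusses separately.
- *The loss falls mainly on gabapentin.* Section 13.1.1 reports how often side effects occur, not how often drug is stopped. Section 7.7.1 provides for dose reduction before stopping. Differential loss is plausible, not documented.
- *The bias is large.* Taking 20% loss on gabapentin, none on placebo and a gap of one SD gives 0.20 × 2.9 = 0.58 points, or 29% of the 2-point target. Nothing in the documents supports that combination; with 5% placebo loss the same gap gives 0.15 × 2.9 = 0.44.
- *The bias must favour gabapentin.* By day 7 men in both arms should be past the three-day dosing period, and nothing shows that men stopped for sedation would then have more pain.

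**Conclusion.** The point holds as an inconsistency that allows avoidable loss of the primary outcome. Sections 7.9 (heading), 7.10, 8 and 8.2 do not make the distinction that 8.1 makes, and section 12.2 has no provision for a missing day-7 score. Under the assumed losses and a 1 to 2 point gap, bias runs from 0.05 to 0.40 points, which is 2.5% to 20% of the 2-point target (0.05/2 and 0.40/2), with type I error between 5.1% and 8.7%. At the low end this is negligible. The issue is more one of bias than of power. The conflict in the text is certain; the size, the split by arm and the direction are not known from the documents. The change is worth making because it is cheap and the lost scores could not be recovered afterwards.

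**What to change.** Reconcile sections 7.9, 7.10, 8, 8.1 and 8.2 so that they distinguish stopping study drug from leaving the study. For outcome-data collection:

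- State that stopping drug for any reason, including an adverse event, non-compliance or inability to take it, does not by itself end participation.
- Add the scheduled REDCap pain and narcotic surveys through post-operative day 7 to the data list in 8.1. This applies to all dosed men unless they withdraw consent, are lost to follow-up, or continued participation is judged not in their best interest.
- In 12.2, state that all available scores are analysed by randomised arm, whether or not drug was stopped, and say how a missing day-7 score is handled.

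When drug is stopped, and when a man is withdrawn for safety, remain for the sponsor to decide; no change to those rules is proposed.

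The cost is amendment wording. Men who stop drug would be asked to finish surveys already scheduled (at most 2 × 3 + 5 × 2 = 16 over the seven days under 11.1 and 12.1), with the staff prompts already planned. No visits are added.

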### **7.11 Measures to Minimize Bias: Randomization and Blinding**

Permuted blocked randomization will be performed. A series of randomized blocks with a defined block size will be generated with a 1:1 allocation ratio to allow for an equal number of participants in the study drug and placebo groups. A statistician from the Weill Cornell CTSC Biostatistics, Epidemiology and Research Design (BERD) Core will create the randomization list and will not be involved with the study statistician(s). The randomization list will also reside in the Research Pharmacy. Only the BERD statistician and the Research Pharmacy will have a copy of the blocked randomization list and will know the true meaning of the block assignments. If unbinding is necessary, the BERD statistician (or Research Pharmacy) can immediately determine whether or not the participant received the study drug or placebo.

### **7.12 Study Intervention/Follow-up Compliance**

Study participant adherence will be completed in the form of a reminder phone call. Participants will be required to complete questionnaires for a visual analogue scale as well as daily narcotic usage.

Participants will be seen for their study materials at their usual post-operative follow-up visit. Two attempts will be made to contact the subject if they do not return for their follow-up visit or provide the necessary study documents, at which point the subject will be considered "lost to follow-up" and no longer participating in the study.

## **8. Study Intervention Discontinuation and Participant Discontinuation/Withdrawal**

Participants may withdraw voluntarily from the study or the PI may discontinue a participant from the study at any time. The following adverse events would necessitate discontinuation of the study intervention or participant discontinuation/withdrawal:

- Drug Reaction with Eosinophilia and Systemic Symptoms (Multiorgan hypersensitivity)
- Anaphylaxis and Angioedema
- Severe Somnolence/Sedation and Dizziness
- Suicidal Behavior and Ideation

Participants may discontinue the study intervention, but remain in the study for follow-up, especially for safety and efficacy study endpoints (if applicable).

### **8.1 Discontinuation of Study Intervention**

Discontinuation from gabapentin administration does not mean discontinuation from the study, and remaining study procedures should be completed as indicated by the study protocol. If a clinically significant finding is identified (including, but not limited to changes from baseline) after enrollment, the investigator or qualified designee will determine if any change in participant management is needed. Any new clinically relevant finding will be reported as an adverse event (AE).

The data to be collected at the time of study intervention discontinuation will include the following:

- Post-operative follow-up to ensure any adverse event resolution

### **8.2 Participant Discontinuation/Withdrawal from the Study**

Participants are free to withdraw from participation in the study at any time upon request.

An investigator may discontinue or withdraw a participant from the study for the following reasons:

- Significant study intervention non-compliance
- If any clinical adverse event (AE), laboratory abnormality, or other medical condition or situation occurs such that continued participation in the study would not be in the best interest of the participant
- If the participant meets an exclusion criterion (either newly developed or not previously recognized) that precludes further study participation
- Participant unable to receive the medication
- Participant lost to follow-up after several attempts to contact subject to schedule study visit.

Subjects will be medically monitored by clinicians in the research team for detection of any adverse events. The reason for participant discontinuation or withdrawal from the study will be recorded on the Case Report Form (CRF). Subjects who sign the informed consent form and are randomized but do not receive the study intervention may be replaced. Subjects who sign the informed consent form, and are randomized and receive the study intervention, and subsequently withdraw, or are withdrawn or discontinued from the study, will not be replaced.

### **8.3 Lost to Follow Up**

A participant will be considered lost to follow-up if he or she fails to return for 1 scheduled visits and is unable to be contacted by the study site staff following 2 attempts.

The following actions must be taken if a participant fails to return to the clinic for a required study visit:

- The site will attempt to contact the participant and reschedule the missed visit within 4 weeks and counsel the participant on the importance of maintaining the assigned visit schedule and ascertain if the participant wishes to and/or should continue in the study.
- Before a participant is deemed lost to follow-up, the investigator or designee will make every effort to regain contact with the participant (where possible, 2 telephone calls and, if necessary, a certified letter to the participant's last known mailing address or local equivalent methods). These contact attempts should be documented in the participant's medical record or study file.
- Should the participant continue to be unreachable, he will be considered to have withdrawn from the study with a primary reason of lost to follow-up.

## **10. Measurement of Effect**

Effect of pain will be measured using the validated numerical rating scale.

Narcotic consumption will be recorded as a numerical value.

### **10.1 Response Criteria**

The study participants will be prompted to complete online surveys administered through REDCap. The REDCap database allows for HIPAA compliant data gathering through this format. Each survey will include the following: a numerical rating scale (0 through 11) to rank current pain, number of narcotic tablets consumed since the prior survey, overall satisfaction of pain control (binary yes/no) as well documentation of other related symptoms (ie. nausea).

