## 1. Protocol Summary

Full Title:	Multi-modal Analgesia to Reduce Narcotics After Scrotal Surgery
Short Title:	Narcotic Reduction After Surgery
Clinical Phase:	III
Principal Investigator:	[name]
Study Description:	The use of non-narcotic multi-modal analgesia to be used in the pre-operative, peri-operative and post-operative period to reduce or potentially eliminate narcotic usage following scrotal surgery. We have shown that the use of anti-inflammatories in the peri-operative period reduce both pain and narcotic use. Our hypothesis is that adding another agent in the multi modal pathway will further reduce pain and potentially reduce narcotic usage.
Sample Size:	N= 86 (43 participants in each arm)
Enrollment:	This study will enroll 86 participants but will screen 114 participants accounting for an approximate 25% screening failure rate.
Study Population:	Participants undergoing microsurgical testicular sperm extraction for non-obstructive azoospermia.
Enrollment Period:	2 years.
Study Design:	Double-blind, placebo-controlled, randomized trial Two study arms (43 participants per arm) Addition of gabapentin pre- and post-operatively
Description of Sites/	
Facilities Enrolling	
Participants:	This will be a single center study at Weill Cornell Medicine/New York Presbyterian Hospital.
Study Duration:	December 31, 2023
Participant Duration:	7 days.
Study Agent/Device Name	
Intervention Description:	Arm #1 – Gabapentin 600mg taken pre-operatively and 300mg taken three times a day for 3 days. Arm #2 – Placebo taken pre-operatively and three times a day for 3 days.
Primary Objective:	Pain scores
Secondary Objectives:	Narcotic consumption
Exploratory Objectives:	Symptom modification (ie. nausea)
Endpoints:	Numerical pain rating scale Narcotic prescription usage

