## 2.4 Risk/Benefit Assessment

### 2.4.1 Known Potential Risks

As per the FDA, gabapentin side effects commonly include dizziness and drowsiness. Other reported adverse events include headache, lack of coordination, viral infection, nausea and vomiting, difficulty speaking, tremor, swelling, fever, jerky movements, difficulty with coordination, double vision and unusual eye movement.

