## **11. Data Reporting / Regulatory Considerations**

### **11.1 Data Collection**

The data collection plan for this study is to utilize REDCap to capture all research intervention procedures outlined in the protocol, toxicity, efficacy, and adverse event data for all enrolled study participants. To ensure maximum compliance, subjects will be prompted by email, phone, or with a text message to their mobile phone. To ensure HIPAA compliance, text messages will only read as "A new survey is due." Participants will be informed of this prompting protocol beforehand. No PHI, or any details of medical therapy, will be revealed in the text message or in the surveys administered through REDCap (please see the survey attachment to review how each survey will appear). Texts will be sent from a study dedicated phone controlled by the study staff. The study phone will be encrypted and managed by ITS per WCM regulation. Subjects will complete surveys at the following intervals: every 8 hours post-operative day 1 and 2, Every 12 hours post-operative day 3 through 7.

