## **12. Statistical Considerations**

### **12.1 Study Design/Endpoints**

The study will be a randomized double blind placebo controlled trial. We will randomize 86 study participants into two arms, with equal numbers in each arm.

Both the control arm and intervention arm will receive medication to be taken 2 hours before surgery as well as for three days three times a day after surgery. The team will be blinded to medication each study participant is receiving and will be recorded using a subject coded system.

Participants will receive reduced oxycodone prescriptions (quantity to be determined by clinical practice and prescribing surgeon) as needed, as well as celecoxib and acetaminophen to be taken as prescribed for the peri-operative period and up to 7 days post-operatively.

During the 7 subsequent post-op days participants in both the intervention and control arms will be asked to maintain a pain diary. The diary will be implemented online through the REDCap platform, which allows for secure online surveys. To ensure maximum compliance, subjects will be prompted by email, phone, or with a text message to their mobile phone. To ensure HIPAA compliance, text messages will only read as "A new survey is due." Participants will be informed of this prompting protocol beforehand. No PHI, or any details of medical therapy, will be revealed in the text message or in the surveys administered through REDCap (please see the survey attachment to review how each survey will appear). Texts will be sent from a study dedicated phone controlled by the study staff. The study phone will be encrypted and managed by ITS per WCM regulation. Subjects will complete surveys at the following intervals: every 8 hours post-operative day 1 and 2, Every 12 hours post-operative day 3 through 7.

Participants will be monitored for adverse events by the pre-operative nurses as well as the post-operative anesthesia care nurses who will be counselled on symptoms to examine for. Participants will have the opportunity to document any adverse events on their surveys.

Our primary endpoint will be to compare participant reported pain between participants receiving gabapentin and those receiving placebo in addition to standard of care. This will be assessed using the 11-point numerical pain rating scales (NRS-11) from post-operative day 1 to 7.

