Our secondary endpoints include narcotic use following surgery including the number of tablets taken, frequency and time when narcotic is initially utilized. Participant satisfaction will be documented. Reduction in other symptoms such as nausea will also be recorded.

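### The diary as described names only nausea, dizziness and somnolence have no standard item during home dosing, and the adverse-event test in 12.2 is not split by event type

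*Combined protocol and SAP*

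**What the plan says.** **Diary content.** Section 10.1 lists a pain rating, tablets taken, a yes/no satisfaction item, "as well documentation of other related symptoms (ie. nausea"). Nausea is the only symptom named. Section 11.1 refers to the form itself ("please see the survey attachment to review how each survey will appear"), but that attachment is not part of the documents available.

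**Nausea as a benefit.** The Protocol Summary gives the exploratory objective as "Symptom modification (ie. nausea"), and 12.1 adds "Reduction in other symptoms such as nausea will also be recorded".

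**Nausea as a harm.** Section 2.4.1 states "Other reported adverse events include headache, lack of coordination, viral infection, nausea and vomiting". Sections 13.1.1 and 15 list GI symptoms among the side effects.

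**Expected harms.** Section 2.4.1 says "gabapentin side effects commonly include dizziness and drowsiness". Section 13.1.1 puts dizziness, somnolence and peripheral edema in its most frequent group, and section 15 has all three on its Minor list.

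**Capture.** In the surveys, "Participants will have the opportunity to document any adverse events on their surveys" (12.1). Pre-operative and recovery nurses are briefed on what to look for (12.1). Staff record events at follow-up calls and clinic visits (15), and the investigator asks about events at each study visit (13.4). Table 1 has no adverse-event row.

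**Analysis.** Section 12.2 plans a chi-square or Fisher's exact test "to compare the proportion of adverse events experienced post-scrotal surgery between the two arms", and a similar analysis for day 1. Section 12.6.1 tabulates toxicities by arm in CTCAE terminology with exact 95% intervals.

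**The concern.** The symptom that the protocol names for the diary is one that gabapentin may reduce, for instance through less oxycodone. The symptoms that gabapentin is most likely to cause are left to open reporting during the three days of home dosing. Nausea is therefore likely to be recorded more completely than dizziness or somnolence.

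The formal comparison does not say which events it counts, or whether nausea is among them. If all events are combined into one yes/no per participant, opposite movements can cancel, and the trial could report similar adverse-event proportions while the pattern of symptoms differs between arms. Tolerability is half of the case for adding a drug to a regimen that already includes celecoxib and acetaminophen, so the reader needs the two kinds of event kept apart.

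**Working it through.** **1. When each capture route operates**

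- Surveys come every 8 hours on days 1 and 2 and every 12 hours on days 3 to 7 (11.1): 3 × 2 + 2 × 5 = 16 surveys. Of these, 3 + 3 + 2 = 8 fall on the home-dosing days 1 to 3.
- The briefed nurses are pre-operative and post-anesthesia staff, so they cover the day of surgery.
- Inquiry at study visits amounts to one post-operative visit (6.1.2.1, 6.1.3, 7.10). It is general and relies on recall.
- Follow-up calls (15) have no stated number, timing or wording. Section 7.12 describes a reminder call for adherence.

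On days 1 to 3 the one instrument with a stated schedule is the diary, and as described it has no dizziness or somnolence item. The day-1 adverse-event comparison in 12.2 leans on it most.

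**2. The sample size behind the comparison**

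The plan gives no adverse-event rate or power. Its only sizing is for pain: 2 points, SD 2.9, 80% power, two-sided 0.05. The two-sample t-test needs 34 per arm, and 34 × 1.25 = 42.5, rounded up to the stated 43. I use 43 per arm below, all evaluable.

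**3. Offsetting in a pooled test (assumed rates)**

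Treat nausea (N) and dizziness or somnolence (D) as independent, with a share s of D captured:

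any-AE = 1 − (1 − N)(1 − s·D)

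Assume D is 10% on placebo and 30% on gabapentin, a true excess of 20 points, and N is 30% on placebo.

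| Comparison | Placebo | Gabapentin | Difference (points) | Power, normal approx. / Fisher |
|---|---|---|---|---|
| D alone, s = 1 | 10.0% | 30.0% | 20 | 64% / 55% |
| Any-AE, N 30% in both arms, s = 1 | 37.0% | 51.0% | 14 | 26% / 19% |
| Any-AE, N 30% vs 20%, s = 1 | 37.0% | 44.0% | 7 | 10% / 7% |
| Any-AE, N 30% vs 20%, s = 0.5 | 33.5% | 32.0% | −1.5 | sign reversed |

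For example, the third row is 1 − 0.70 × 0.90 = 0.370 and 1 − 0.80 × 0.70 = 0.440. Pooling dilutes the excess even when nausea is equal, and a fall in nausea dilutes it further. Incomplete capture also hurts the separate comparison: at s = 0.5 the excess in D alone is 10 points, with power 34% / 21%.

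**4. What a separate comparison can achieve for a smaller excess**

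One reading of the 8% figure in 13.1.1 is an 8-point excess over placebo. Assume 5% versus 13%:

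- Unpooled standard error: √[(0.13 × 0.87 + 0.05 × 0.95)/43] = 0.0611
- Pooled standard error: √[0.09 × 0.91 × 2/43] = 0.0617
- Power with pooled variance under the null: Φ[(0.08 − 1.96 × 0.0617)/0.0611] = Φ(−0.67) = 25%
- Power with unpooled variance: Φ(0.08/0.0611 − 1.96) = Φ(−0.65) = 26%
- Fisher's exact test: 13%
- 95% CI half-width: 1.96 × 0.0611 = 0.12, so 8 points would be reported as roughly −4 to 20

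With 10% versus 18% the power is 18% (Fisher 12%).

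**The case against.** **The form may already ask.** The survey attachment is cited but was not available, and the protocol uses the abbreviation before nausea loosely: section 15 uses it before varicocele, which is not the only infertility diagnosis. Section 12.1 introduces nausea as an example. A reader might infer that the diary asks about nothing but nausea; the documents do not establish that. The point stands only for the diary as described.

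**Other routes exist.** A reader might also infer that dizziness and somnolence rest entirely on spontaneous report. That is wrong for the plan as a whole, given the briefed nurses, the calls, the visit inquiry and the naming of both events in section 15. What stands is that none of these routes is a standard, named question during home dosing.

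**The pooled test is one reading.** Section 12.2 defines no any-event composite and does not say that the nausea item feeds it. The objectives already place nausea under symptom modification. The CTCAE tabulation in 12.6.1 can show dizziness and somnolence separately with intervals. This is the strongest reply, and it confines the masking to the test in 12.2. It does not help with events that were never elicited.

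**The rates are assumed.** Any example in which nausea falls about as much as dizziness rises cancels by construction. The figures above show that offsetting is possible and do not predict it.

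**Conclusion.** The point holds as a gap in specification. The protocol describes no standard dizziness or somnolence item for home dosing, gives nausea two roles without saying which applies in the adverse-event test, and leaves the event type in that test open. Under an any-event reading, a fall in nausea can offset a rise in dizziness or somnolence in that one result. The documents do not support the stronger conclusions that the trial will hide the harm or that its safety data will be uninterpretable, because 12.6.1 can report events by term.

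The size is unknown. The illustration rests on assumed rates, independent events, an assumed capture share and 43 evaluable participants per arm. Nor would separating the events make the test sensitive: for an 8-point excess, power is about 13 to 26% at an assumed 5% versus 13%. The gain is fuller capture and estimates that can be read, which makes this a cheap improvement to secondary safety reporting. It does not threaten the primary analysis.

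**What to change.** 1. Check the survey form. If it lacks them, add fixed yes/no items for the section 15 Minor events, at least dizziness and somnolence, to the existing REDCap survey. Word any GI item so that it does not duplicate nausea. If the form already has these items, say so in 10.1.
2. In 12.2, report dizziness/somnolence and nausea as separate between-arm differences with 95% confidence intervals, overall and for day 1.
3. State in 12.2 that the between-arm comparison of nausea belongs to symptom modification. Adverse-event logging and reporting of nausea need not change.
4. Do not rest the tolerability conclusion on one pooled adverse-event proportion or on a non-significant test.

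The cost is a survey edit and a few sentences in 12.2, with no added staff or visits. Participants get a few more tick boxes. Solicited rates will be higher in both arms and less comparable with trials that use spontaneous reports.
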